2.10 PD and PK/PD analyses

The potential relationship between asciminib exposure (e.g. trough concentration) and efficacy, pharmacodynamics (PD) or safety endpoints may be assessed by graphic exploration and/or statistical modeling, as appropriate, including effect of population covariates. Additional exposure-response analyses for ECG may be conducted. The concentration data may be analyzed by a population approach to evaluate the influence of covariates on drug exposure. If applicable, the details of the above-mentioned analyses will be described in a separate analysis plan and reported separately.

The relationship between average trough plasma concentration up to 24 weeks and BCR-ABL ratio IS (%) at 24 weeks will be assessed by graphic exploration.

2.11 Patient-reported outcomes

The FAS will be used for analyzing PRO data unless specified differently. The MDASI CML, PGIC along with EQ-5D-5L will be used to assess patient's disease-related symptoms and health-related quality of life from baseline to EOT; and the WPAI-CML will be used to assess work productivity and activity impairment related to the patient's CML. All tools require patient's direct completion and will be administered utilizing electronic device for data collection at scheduled time points from screening to end of treatment.

The baseline is defined in [Section 2.1.1](#). Patients with an evaluable baseline score and at least one evaluable post-baseline score during the treatment period will be included in the change from baseline analyses. Missing data items in a scale will be handled according to the manual for each instrument. No imputation will be applied if the total or subscale scores are missing at a visit. All measures will assess differences between the treatment arms.

Compliance to the schedule of administration of each PRO questionnaire will be summarized by treatment group, for baseline and scheduled post-baseline assessment time points. The following categories, as collected on the eCRF, will be used to describe whether the questionnaire was completed at a specific time point:

1. yes, fully completed
2. yes, partly completed
3. no

Repeated measures model for continuous scores

To best utilize the repeated assessments of a given PRO score, a repeated measures model for longitudinal data will be used to estimate differences between treatment arms. This repeated measures model will include terms for treatment, the stratification factor (major cytogenetic response status), time, baseline value as main effects, and an interaction term for treatment by time. This analysis will be restricted to patients with an evaluable baseline score and at least

one evaluable post-baseline score. All data collected until end of treatment (including the end of treatment assessment) will be included in the analysis. Note that only data collected under treatment (i.e. while the patient is treated) will be included. The end of treatment assessment will be included if collected within 7 days of the last dose intake.

Time will be considered as a continuous variable expressed in weeks, i.e. considering that the PRO score follow a linear trend.

As a first approach, an unstructured correlation matrix will be used to model the correlation within patients. The structure of the correlation matrix will be investigated and simplified using likelihood ratio tested if appropriate.

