2.11.1 MDASI-CML

The M.D. Anderson Symptom Inventory – Chronic Myeloid Leukemia (MDASI-CML) questionnaire is planned to be administered during screening, at weeks 4, 8, 12, 16, 24, 36, 48 and 96 after randomization.

The MDASI-CML is a 26 item self-administered questionnaire for adult CML patients. Twenty of the items measure the severity of disease-related symptoms and are scored from 0 (Not present) to 10 (As bad as you can imagine) and 6 items that measure symptom interference with daily life scored from 0 (Did not interfere) to 10 (Interfered completely).

The severity score will be calculated when a patient scores at least 11 items out of the 20 severity items using the formula: (sum of scores for the items answered) / (number of items answered). If a patient scores fewer than 11 items, the severity score will be missing.

The interference score will be calculated when a patient scores at least 4 items out of the 6 interference items using the formula: (sum of scores for the items answered) / (number of items answered). If a patient scores fewer than 4 items, the interference score will be missing.

For the severity score and interference score, descriptive statistics (n, mean, SD, median, 25th and 75th percentiles) by treatment arm will be provided for the actual scores and changes from baseline scores at each scheduled assessment time point.

Between-treatment differences for the change in severity and interference scores will be evaluated using the above-mentioned repeated measures model.

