2.11.2 EQ-5D-5L

EQ-5D-5L is a two-part standardized instrument for measuring health outcomes in a wide range of health conditions and treatments. It consists of a descriptive system and a visual analogue scale (EQ VAS). The descriptive system comprises the following 5 dimensions: mobility, self-care, usual activities, pain/discomfort and anxiety/depression. Each dimension has 5 levels: no problems, slight problems, moderate problems, severe problems and extreme problems (or unable to perform the activity). The EQ VAS records the respondent's self-rated health on a vertical, visual analogue scale where the endpoints are labeled 'Best imaginable health state' and 'worst imaginable health state'.

The EQ-5D-5L data will be used to calculate utility values for the economic evaluation of asciminib and bosutinib in a separate analysis.

The EQ-5D-5L questionnaire is planned to be administered during screening, at weeks 4, 8, 12, 16, 24, 36, 48 and 96 after randomization.

Descriptive system

The number and percentage of subjects in the five levels of each EQ-5D dimension will be presented by treatment group at each assessment time point.

EQ VAS

The EQ VAS records the respondent's self-rated health on a vertical, visual analogue scale from 0, labeled as 'worst imaginable health state', to 100, labeled as 'best imaginable health state'.

For the EQ VAS, descriptive statistics (n, mean, SD, median, 25th and 75th percentiles) by treatment arm will be provided for actual values and for the change from baseline at each assessment time point.

Between-treatment differences for the changes in EQ VAS score will be evaluated using the above-mentioned repeated measures model.

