2.11.3 WPAI-CML

The Work Productivity and Activity Impairment Questionnaire – Chronic Myeloid Leukemia (WPAI-CML) questionnaire is planned to be administered during screening, at weeks 4, 12, 24, 48 and 96 after randomization.

The WPAI-CML is a six-item questionnaire which is intended to measure work and activity impairment associated with CML for those who self-identify as currently employed for pay. This questionnaire measures self-reported productivity loss associated with CML during the past seven days. It consists of questions about absence from work due to CML, hours spent at work, the reduction in productivity at work attributed to CML, and the reduction in productivity while performing regular activities. WPAI-CML outcomes are expressed as impairment percentages, with higher numbers indicating greater impairment and less productivity, i.e., worse outcomes. Scoring will be done according to WPAI-CML instrument guidance resulting in four scores including: Percent work time missed due to problem; percent impairment while working due to problem; Percent overall work impairment due to problem; and, percent activity impairment due to problem.

Descriptive statistics (n, mean, SD, median, 25th and 75th percentiles) for each of the four derived outcome scores and changes from baseline scores will be presented by treatment arm at each scheduled assessment time point with .

Between-treatment differences for the changes in each of the four outcome scores will be evaluated using the above-mentioned repeated measures model.

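### The PRO repeated-measures model fixes a straight line in time over 96 weeks, with no linearity check and no named week for the contrast; if the arm difference is not linear, its estimates are biased

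*Combined protocol and SAP*

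**What the plan says.** SAP Section 2.11 states the purpose of the model: "a repeated measures model for longitudinal data will be used to estimate differences between treatment arms". Its fixed effects are "terms for treatment, the stratification factor (major cytogenetic response status), time, baseline value as main effects, and an interaction term for treatment by time", and the form of time is set explicitly: "Time will be considered as a continuous variable expressed in weeks, i.e. considering that the PRO score follow a linear trend". On the covariance it says "As a first approach, an unstructured correlation matrix will be used to model the correlation within patients"; that matrix may then be simplified. Nothing similar is planned for the mean trend, and no week is named at which the model-based difference will be read. The wording is the same in the 2017 SAP, in the amended SAP of August 2020 and in the addendum of October 2020.

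The schedule is in Sections 2.11.1 to 2.11.3. MDASI-CML is "planned to be administered during screening, at weeks 4, 8, 12, 16, 24, 36, 48 and 96 after randomization", EQ-5D-5L follows the same weeks, and WPAI-CML is "planned to be administered during screening, at weeks 4, 12, 24, 48 and 96 after randomization". Those sections send the between-arm comparison of the two MDASI-CML scores, EQ VAS and the four WPAI scores to this one model. They also plan descriptive summaries by arm at each visit, without a between-arm contrast. Table 1-1 lists the PRO comparison as exploratory.

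**The concern.** Two parameters, a gap in intercept and a gap in slope, carry the whole model-based PRO comparison across Weeks 4 to 96. Five of the eight MDASI-CML and EQ VAS visits fall at or before Week 24, and none falls between Weeks 48 and 96. A tolerability or symptom difference could plausibly appear early and fade, or build up and then level off. A straight line cannot follow either course: it spreads the misfit over the visits, and the distant Week 96 visit pulls strongly on the slope. Nothing planned in the model would reveal the misfit, and with no week named the reported difference could be read at a point where the error is large.

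At stake is the interpretation of the PRO comparison: an early benefit or harm could be understated, or a difference shown where there is none.

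**Working it through.** The SAP gives no sample size, standard deviation or expected trajectory for the PRO model, so it has no PRO figure to reproduce. The visit weeks come from Sections 2.11.1 to 2.11.3. The difference profiles, correlations and retention rates below are assumptions.

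**1. Influence of each visit (complete data; independence or compound symmetry).** For MDASI-CML and EQ VAS:

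- Mean visit time = (4+8+12+16+24+36+48+96)/8 = 30.5 weeks.
- Sxx = Σ(t − 30.5)² = 702.25 + 506.25 + 342.25 + 210.25 + 42.25 + 30.25 + 306.25 + 4290.25 = 6430.
- Week 96 share = 4290.25/6430 = 66.7%. The next largest is Week 4, at 702.25/6430 = 10.9%.
- Week 96 leverage = 1/8 + 0.667 = 0.79, against an average of 2/8 = 0.25.

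For WPAI-CML the mean is 184/5 = 36.8 and Sxx is 5484.8. The Week 96 share is 59.2²/5484.8 = 63.9%, with leverage 1/5 + 0.639 = 0.84 against an average of 0.40.

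**2. What the line makes of a nonlinear difference.** With the same visit pattern in both arms, the fitted arm difference is the projection of the true difference d(t) on intercept and slope. Under independence or compound symmetry, slope = Σ(t − 30.5)d(t)/6430, and the line passes through the mean of d at 30.5 weeks.

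*Early effect that fades:* d = −1 at Weeks 4 to 16, −0.5 at Week 24 and 0 afterwards.

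- Mean d = −4.5/8 = −0.5625.
- Slope = (26.5 + 22.5 + 18.5 + 14.5 + 3.25)/6430 = 85.25/6430 = 0.01326 per week.
- Fitted at Week 48: −0.5625 + 0.01326 × 17.5 = −0.33 (true 0).
- Fitted at Week 96: −0.5625 + 0.01326 × 65.5 = +0.31 (true 0).

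*Ramp to a plateau:* d = 0, −0.2, −0.4, −0.6 at Weeks 4, 8, 12, 16 and −1 from Week 24.

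- Mean d = −5.2/8 = −0.65.
- Slope = (4.5 + 7.4 + 8.7 + 6.5 − 5.5 − 17.5 − 65.5)/6430 = −61.4/6430 = −0.00955 per week.
- Fitted at Week 4: −0.65 + 0.00955 × 26.5 = −0.40 (true 0).
- Fitted at Week 24: −0.65 + 0.00955 × 6.5 = −0.59 (true −1).

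**3. Dependence on correlation.** The plan starts from an unstructured matrix, so the projection was repeated by generalised least squares, b = (X′V⁻¹X)⁻¹X′V⁻¹d, with autoregressive V (correlation ρ per 12 weeks).

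| Assumed correlation | Early effect, Week 48 | Early effect, Week 96 | Ramp, Week 24 |
|---|---|---|---|
| Truth | 0 | 0 | −1 |
| Independence or compound symmetry | −0.33 | +0.31 | −0.59 |
| ρ = 0.7 | −0.37 | +0.15 | −0.47 |
| ρ = 0.9 | −0.44 | +0.08 | −0.33 |

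Under serial correlation the slope rests on the two end visits. Weeks 4 and 96 carry 38% and 47% of the absolute slope weight at ρ = 0.7, and 48% and 49% at ρ = 0.9.

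**4. Dependence on who reaches Week 96.** Retention is not given. If the contributing fraction declines linearly to Week 96, the Week 96 share of weighted Sxx is 66% at 80% retention, 60% at 40%, 49% at 20%, 35% at 10% and 22% at 5%. Section 2.1 sets the primary cut-off at 24 weeks after the last patient's first dose, so the lower fractions are the relevant ones for that analysis.

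**5. When there is no error.** A constant difference from Week 4, or one exactly linear in weeks, lies in the span of intercept and slope. The error is then 0 at every visit under every correlation tried. With categorical visit and treatment-by-visit, the arm difference is free at each visit and the shape error is 0 for any profile.

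**The case against.** The strongest defence is that the error is conditional. The documents give no expected PRO course, so both profiles above are illustrations, and a constant or linear difference is estimated correctly. A nonlinear course shared by both arms does not by itself bias the difference when visit patterns match. This stands: a reader might infer that the planned differences are wrong as a matter of fact, or wrong at every visit, and the documents do not support that.

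Second, the SAP does not promise a model-based difference at each visit, and it does plan descriptive summaries at each visit in which a nonlinear pattern could be seen. That also stands, but the summaries carry no between-arm interval, and the unnamed week is itself a gap.

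Third, the leverage figures assume complete data and independence or compound symmetry. End-of-treatment assessments within 7 days of the last dose also enter, at other times, and are left out here. So a reader should not infer that Week 96 alone drives the slope in every analysis: its share is smaller at the primary cut-off, and under strong serial correlation Week 4 matters about as much.

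Fourth, the PRO comparison is exploratory. The formal tests are of MMR at 24 and 96 weeks only.

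**Conclusion.** The point holds in conditional form. If the arm difference is not linear over Weeks 4 to 96, the model-based PRO differences are biased, and the plan has no check on the mean trend that would show it. In the two assumed profiles, with complete data, a difference that has vanished is still fitted as -0.33 to -0.44 at Week 48, and a full effect of -1 at Week 24 is fitted as -0.33 to -0.59. The flexible correlation matrix does not protect the mean model.

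Two further inferences are not supported. The fitted +0.08 to +0.31 at Week 96 is a spurious difference where the true value is 0; it is not a reversal of a real effect. And although Week 96 is observed only in patients still on treatment, that follows from the on-treatment data rule and would remain under categorical visits.

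No confirmatory conclusion is affected. The change is worth making because it is cheap and removes an assumption that the SAP does not justify.

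**What to change.** For the MDASI-CML scores, EQ VAS and the WPAI-CML scores, replace linear time with visit as a categorical factor. Use the windows in Tables 2-3 and 2-4, which Section 2.1.1 already sets up for longitudinal analysis. Include treatment-by-visit and keep the unstructured covariance. Report the treatment difference with its 95% confidence interval at named weeks, for example Weeks 24, 48 and 96. The linear-time model can stay as a sensitivity analysis.

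The cost is SAP wording and a model statement; data and software are unchanged. The treatment difference takes eight parameters instead of two (five for WPAI-CML), and some precision is lost if the trend is truly linear. The addendum of October 2020 postdates the primary database lock, so the change should be dated and recorded as made after that lock and before the 96-week analysis. It does not address the on-treatment selection at Week 96, which should be stated as a limitation.

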2.11.1 MDASI-CML

The M.D. Anderson Symptom Inventory – Chronic Myeloid Leukemia (MDASI-CML) questionnaire is planned to be administered during screening, at weeks 4, 8, 12, 16, 24, 36, 48 and 96 after randomization.

The MDASI-CML is a 26 item self-administered questionnaire for adult CML patients. Twenty of the items measure the severity of disease-related symptoms and are scored from 0 (Not present) to 10 (As bad as you can imagine) and 6 items that measure symptom interference with daily life scored from 0 (Did not interfere) to 10 (Interfered completely).

The severity score will be calculated when a patient scores at least 11 items out of the 20 severity items using the formula: (sum of scores for the items answered) / (number of items answered). If a patient scores fewer than 11 items, the severity score will be missing.

The interference score will be calculated when a patient scores at least 4 items out of the 6 interference items using the formula: (sum of scores for the items answered) / (number of items answered). If a patient scores fewer than 4 items, the interference score will be missing.

For the severity score and interference score, descriptive statistics (n, mean, SD, median, 25th and 75th percentiles) by treatment arm will be provided for the actual scores and changes from baseline scores at each scheduled assessment time point.

Between-treatment differences for the change in severity and interference scores will be evaluated using the above-mentioned repeated measures model.

2.11.2 EQ-5D-5L

EQ-5D-5L is a two-part standardized instrument for measuring health outcomes in a wide range of health conditions and treatments. It consists of a descriptive system and a visual analogue scale (EQ VAS). The descriptive system comprises the following 5 dimensions: mobility, self-care, usual activities, pain/discomfort and anxiety/depression. Each dimension has 5 levels: no problems, slight problems, moderate problems, severe problems and extreme problems (or unable to perform the activity). The EQ VAS records the respondent's self-rated health on a vertical, visual analogue scale where the endpoints are labeled 'Best imaginable health state' and 'worst imaginable health state'.

The EQ-5D-5L data will be used to calculate utility values for the economic evaluation of asciminib and bosutinib in a separate analysis.

The EQ-5D-5L questionnaire is planned to be administered during screening, at weeks 4, 8, 12, 16, 24, 36, 48 and 96 after randomization.

Descriptive system

The number and percentage of subjects in the five levels of each EQ-5D dimension will be presented by treatment group at each assessment time point.

EQ VAS

The EQ VAS records the respondent's self-rated health on a vertical, visual analogue scale from 0, labeled as 'worst imaginable health state', to 100, labeled as 'best imaginable health state'.

For the EQ VAS, descriptive statistics (n, mean, SD, median, 25th and 75th percentiles) by treatment arm will be provided for actual values and for the change from baseline at each assessment time point.

Between-treatment differences for the changes in EQ VAS score will be evaluated using the above-mentioned repeated measures model.

2.11.3 WPAI-CML

The Work Productivity and Activity Impairment Questionnaire – Chronic Myeloid Leukemia (WPAI-CML) questionnaire is planned to be administered during screening, at weeks 4, 12, 24, 48 and 96 after randomization.

The WPAI-CML is a six-item questionnaire which is intended to measure work and activity impairment associated with CML for those who self-identify as currently employed for pay. This questionnaire measures self-reported productivity loss associated with CML during the past seven days. It consists of questions about absence from work due to CML, hours spent at work, the reduction in productivity at work attributed to CML, and the reduction in productivity while performing regular activities. WPAI-CML outcomes are expressed as impairment percentages, with higher numbers indicating greater impairment and less productivity, i.e., worse outcomes. Scoring will be done according to WPAI-CML instrument guidance resulting in four scores including: Percent work time missed due to problem; percent impairment while working due to problem; Percent overall work impairment due to problem; and, percent activity impairment due to problem.

Descriptive statistics (n, mean, SD, median, 25th and 75th percentiles) for each of the four derived outcome scores and changes from baseline scores will be presented by treatment arm at each scheduled assessment time point with .

Between-treatment differences for the changes in each of the four outcome scores will be evaluated using the above-mentioned repeated measures model.

2.11.4 PGIC

The Patient Global Impression of Change (PGIC) instrument is planned to be administered during at weeks 4, 8, 12, 16, 24, 36, 48 and 96 after randomization

The PGIC is comprised of a single question intended to measure a patient's perspective of improvement or deterioration over time relative to treatment. The PGIC uses a seven-point scale

where one (1) equals very much improved and seven (7) equals very much worse. Missing values will not be imputed.

The number and percentage of subjects in each of the seven categories for PGIC will be presented by treatment group at each assessment time point.

2.12 Resource utilization

Data relating to resource utilization (described in trial protocol Section 7.2.5) from the FAS will be used for the purpose of economic evaluation, which will be carried out and reported as a separate activity outside the CSR.

The measures of healthcare resource utilization (HCRU) include: hospitalization (H), emergency room (ER) visit, general practitioner (GP) visits, specialist (Sp) visit and urgent care (UC) visit. HCRU will be assessed as follows: frequency and duration of hospitalization from baseline up to end of treatment; frequency of emergency room visits from baseline up to end of treatment; frequency of additional outpatient office visits general practitioner, specialist, and urgent care visits from baseline up to end of treatment. Hospitalization visits will also record the number of days on ward and the type of ward (hospital unit) and the discharge status. At each HCRU collected, the reason for the visit, i.e. related to CML, AE related to CML therapy or other reason, will be collected, in order to quantify the impact of treatment on healthcare resources.

HCRU data by treatment arm will be summarized in the primary analysis CSR and the end of study treatment CSR, with descriptive statistics (n, mean, median, SD, min, max) for quantitative variables, and count and percentage for qualitative variables.

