5.6	Statistical models	71
5.6.1	Primary analysis	71
5.6.2	Key secondary analysis	72
5.6.3	Other analyses	73
5.6.4	Calculation of exposure-adjusted incidence rate.....	74
6	Reference	74

List of abbreviations

AE	Adverse event
AESI	Adverse event of special interest
ALP	Alkaline phosphatase
ALT	Alanine aminotransferase
AP	Accelerated phase
AST	Aspartate aminotransferase
ATC	Anatomical therapeutic classification
AUC	Area under the curve
BC	Blast crisis
bid	bis in diem/twice a day
CCyR	Complete cytogenetic response
CHR	Complete hematologic response
CMH	Cochrane-Mantel-Haenszel
CML	Chronic myelogenous leukemia
CML-CP	Chronic myelogenous leukemia in chronic phase
CRO	Contract research organization
CSP	Clinical study protocol
CSR	Clinical study report
CTCAE	Common terminology criteria for adverse events
CV	Coefficient of variation
DAR	Dosage administration record
DI	Dose intensity
DMC	Data monitoring committee
DRL	Drug reference listing
DSUR	Development safety update report
ECG	Electrocardiogram
eCRF	Electronic case report form
EOT	End of treatment in the treatment phase (patient level)
EOsT	End of study treatment (study level)
ER	Emergency room
FAS	Full analysis set
FD	First dose date of study treatment during the treatment phase
FD _{switch}	First dose date of asciminib during the treatment switch phase
GP	General practitioner
H	Hospitalization
HCRU	Health care resource utilization
HLT	High level term
HLGT	High level group term
IRT	Interactive response technology
IS	International scale
LD	Last dose date of study treatment during the treatment phase
LD _{switch}	Last dose date of asciminib during the treatment switch phase

LLOQ	Lower limit of quantitation
LPFT	Last patient first treatment
LSC	Leukemic stem cell
LVEF	Left ventricular ejection fraction
MCyR	Major cytogenetic response
mCyR	Minor cytogenetic response
MedDRA	Medical dictionary for regulatory activities
MMR	Major molecular response
NCI	National Cancer Institute
NGS	Next generation sequencing
NMQ	Novartis MedDRA Query
OS	Overall survival
PAS	Pharmacokinetic analysis set
PCR	Polymerase chain reaction
PCyR	Partial cytogenetic response
PD	Pharmacodynamic
PDI	Planned dose intensity
PFS	Progression-free survival
Ph+	Philadelphia chromosome positive
PK	Pharmacokinetics
PPS	Per-protocol set
PRO	Patient-reported outcomes
PSUR	Periodic safety update report
PT	Preferred term
qd	Quaque die / once a day
RDI	Relative dose intensity
SAE	Serious adverse event
SAP	Statistical analysis plan
SD	Standard deviation

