To characterize mutations in the BCR-ABL1 gene at Week 1 Day 1, upon confirmed loss of MMR and/or at end of treatment and examine their association with molecular and cytogenetic response for asciminib vs bosutinib	BCR-ABL1 gene mutations at Week 1 Day 1, upon confirmed loss of MMR and/or at end of treatment as determined by Sanger Sequencing
To understand biology of CML and bone marrow microenvironment on leukemic stem cells (LSCs) eradication, including patients' immunogenicity	Bone marrow biopsies characterization for adaptive immune response by immunohistochemistry (IHC); bone marrow aspirates to evaluate the effect of treatments on LSCs burden and immune cells subsets changes by flow cytometry
To assess clonal evolution during treatment with asciminib vs. bosutinib	Low level BCR-ABL1 mutation profiles assessed by mass spectrometry at Week 1 Day 1, upon confirmed loss of MMR and/or at EOT. Clonal evolution of several genes implicated in CML assessed by Next Generation Sequencing (NGS) methods
To evaluate soluble/inflammatory factors that correlate with response to asciminib vs. bosutinib treatment	Baseline and changes from baseline of cytokine expression in plasma
To compare the impact of treatment on patient reported outcomes (PRO) including CML-specific symptoms, patient quality of life, and impact on work productivity and activity impairment from baseline and EOT between treatment arms in all patients	Change in symptom burden and interference from baseline over time according to the MDASI-CML PRO instrument Change in patient's impression of CML symptoms according to Patient Global Impression of Change (PGIC) Change in health utility from baseline over time according to EQ-5D-5L Change in work productivity and activity impairment over time according to WPAI
To compare the impact of treatment on health care resource utilization between treatment arms in all patients	Health care resource burden over time

2 Statistical methods

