2.8.1 Adverse events (AEs)

AE summaries will include all AEs occurring during the on-treatment period (or the on-switched treatment period). All AEs collected in the AE eCRF page will be listed along with the information collected on those AEs e.g. AE relationship to study drug, AE outcome, etc. AEs with start date outside of the on-treatment period will be flagged in the listings.

AEs will be summarized by number and percentage of subjects having at least one AE, having at least one AE in each primary system organ class (SOC) and for each preferred term (PT) using MedDRA coding. A subject with multiple occurrences of an AE will be counted only once in the respective AE category. A subject with multiple CTCAE grades or the same preferred term will be summarized under the maximum CTCAE grade recorded for the event. AE with missing CTCAE grade will be included in the 'All grades' column of the summary tables.

In AE summaries, the primary system organ class will be presented alphabetically and the preferred terms will be sorted within primary SOC in descending frequency. The sorting order for the preferred term will be based on their frequency in the asciminib arm.

The following adverse event summaries will be produced by treatment arm for the Safety set and Switch Analysis Set: overview of adverse events and deaths, AEs by SOC and PT, summarized by relationship, seriousness, leading to treatment discontinuation, leading to dose interruption/adjustment, requiring additional therapy, and leading to fatal outcome. The study treatment-related AEs/SAEs/AEs leading to treatment discontinuation as well as SAE with fatal outcome are summarized for the Safety set and Switch Analysis set.

For posting to ClinTrial.gov and EudraCT, a summary table of on-treatment deaths and serious AEs and another summary table of non serious AEs by treatment, both including occurrences (an occurrence is defined as >1 day between start and prior end date of record of same preferred term) and sorted by SOC and PT, will be presented as well.

In order to account for differences in exposure between the treatment arms, incidence rates of AEs and SAEs will be presented by adjusting for duration of treatment period in patient-years. They will also be reported by time intervals (i.e. period of emergence: the event is assigned to the interval when it first started): 0 to 2 months, > 2 months to 6 months, > 6 months to 12 months, >12 months and more after the start of study treatment.

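### Resource use is summarized by arm without adjusting for time on treatment, so an arm whose patients stop earlier will appear to use less care at equal true rates

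*Combined protocol and SAP*

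**What the plan says.** Table 1-1 of the SAP (section 1.2) lists an exploratory objective: "To compare the impact of treatment on health care resource utilization between treatment arms in all patients".

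Section 2.12 sets the window for each resource type. Hospitalization is covered as "frequency and duration of hospitalization from baseline up to end of treatment", emergency room use as "frequency of emergency room visits from baseline up to end of treatment", and the outpatient group (general practitioner included) ends with "specialist, and urgent care visits from baseline up to end of treatment". The SAP's list of abbreviations defines end of treatment at patient level and keeps a separate term for the study-level end of study treatment. The window therefore closes on a different date for each patient.

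The full analysis set is used. The primary and end-of-study-treatment reports give results by arm "with descriptive statistics (n, mean, median, SD, min, max) for quantitative variables, and count and percentage for qualitative variables". The section mentions no rate, person-time denominator, offset, fixed period or censoring rule. The economic evaluation is a different exercise, "which will be carried out and reported as a separate activity outside the CSR". The 2017 SAP, the August 2020 amendment and the October 2020 addendum agree on all of this.

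For adverse events, section 2.8.1 of the amended SAP and the addendum introduces patient-year incidence rates "In order to account for differences in exposure between the treatment arms", and section 5.6.4 gives the calculation.

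**The concern.** Visits, admissions and hospital days accumulate with time observed. If each patient's count stops at that patient's end of treatment, the mean per patient reflects both how often patients use care and how long they stay on treatment. The planned table does not separate the two, yet its stated purpose is to compare arms.

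The SAP itself treats unequal exposure as likely enough to plan for. Its document history says the adjusted adverse event rates were added because exposure might differ between arms, and section 2.3.1 tabulates discontinuation before Weeks 24, 48 and 96 by arm. Section 1.1 also offers a switch to asciminib after treatment failure to bosutinib patients only. That switch ends the patient's randomized treatment phase, and later use then falls outside the section 2.12 window.

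What is at stake is the reading of the resource-use tables in two study reports. A lower mean in one arm could be taken as less need for care when it partly or wholly reflects shorter observation.

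**Working it through.** The documents state no resource-use figure, so there is none to reproduce. The check is a reading of the text followed by an illustration.

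**Text.** For adverse events and for resource use, the quantity counted grows with time on treatment. Sections 2.8.1 and 5.6.4 divide adverse event incidence by patient-years; section 2.12 divides by nothing. Section 2.4.1 derives total patient-years of exposure per group, but on the Safety Set and from first to last dose, and nothing links it to resource use, which is on the full analysis set from baseline to end of treatment.

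**Illustration.** Inputs:
- Horizon T of 96 weeks: 96 × 7 / 365.25 = 1.84 years. Treatment can run longer under section 1.1, so this is a simplification.
- The same true rate of use per year, λ, in both arms (assumed).
- The proportion S still on treatment at 96 weeks, with exponential discontinuation (assumed; the documents give no retention by arm).

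Formulas: hazard h = −ln(S) / T; mean observed time m = (1 − S) / h; expected mean count = λ × m. At equal λ, the apparent ratio of mean counts is m(earlier-stopping arm) / m(longer-treated arm).

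For S = 60%: h = 0.511 / 1.84 = 0.278 per year, and m = 0.40 / 0.278 = 1.44 years. Against that arm:

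| Assumed S, earlier-stopping arm | m (years) | Apparent ratio | True rate ratio needed to look equal |
|---|---|---|---|
| 60% | 1.44 | 1.00 | 1.00 |
| 50% | 1.33 | 0.92 | 1.09 |
| 40% | 1.20 | 0.84 | 1.20 |
| 30% | 1.07 | 0.74 | 1.35 |
| 20% | 0.91 | 0.63 | 1.58 |

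Other assumed pairs fall within the same range: 70% v 50% gives 0.86, 70% v 30% gives 0.69, 50% v 40% gives 0.91, and 80% v 40% gives 0.73.

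**If the earlier-stopping arm truly uses more care.** Apparent ratio = true rate ratio × ratio of mean times. At 60% v 30%, a true ratio of 1.20 appears as 1.20 × 0.74 = 0.89 (direction reversed), and a true ratio of 1.50 appears as 1.50 × 0.74 = 1.11 (understated).

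**With a person-time denominator.** Events / time = (n × λ × m) / (n × m) = λ. Equal true rates then give a ratio of 1.00 at any retention.

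**The case against.** The strongest reply is that section 2.12 may not be the whole plan. It refers to protocol section 7.2.5, and the protocol amendment history shows a section 10.6.4.1 on resource utilization whose reporting duration was corrected. Neither text was available, so a rate-based analysis there cannot be excluded. Section 2.12 also says what will be assessed, not what is collected; a reader might infer that collection itself stops at end of treatment, but the available text does not settle that.

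A reader might also infer that the earlier-stopping arm will look cheaper. The documents do not support that: the planned tables contain no costs, no test and no between-arm estimate, and the economic evaluation, whose method is not shown, may handle time.

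It can be added that a reader could divide event totals by the exposure summary in section 2.4.1. That gives only an approximation, because the analysis set and time window differ, and it leaves the reader to supply the comparison the objective calls for.

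Finally, rates per patient-year are not free of bias. If visits cluster early or around the event that ends treatment, the rate is inflated in the arm that stops sooner. This stands, and is a reason to show both summaries. None of these points supplies an adjustment in section 2.12 itself.

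**Conclusion.** The point holds for the tables specified in SAP section 2.12: unadjusted per-patient summaries over a window that ends at each patient's end of treatment cannot separate rate of use from time on treatment. The direction, lower apparent use in the earlier-stopping arm, requires that time on treatment differs by arm and that rates per unit time are similar; with a large enough true excess, the effect only shrinks the difference.

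The size is unknown. The range 0.63 to 0.92 depends entirely on assumed retention and exponential discontinuation over 96 weeks. A reader might choose mean treatment times such as 24 against 8 months and infer a threefold distortion (24 / 8 = 3), but nothing in the documents supports those times, or states which arm stops earlier.

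The consequence is limited: an exploratory, descriptive output that does not touch the primary or key secondary tests. It is a worthwhile, inexpensive improvement, subject to what protocol sections 7.2.5 and 10.6.4.1 say.

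**What to change.** In section 2.12, add for each resource type and arm the total events, and total hospital days, divided by total observation time from baseline to end of treatment (or to data cut-off for patients still on treatment), per patient-year. Keep the planned summaries alongside, and label both as on-treatment use.

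State three conventions: the date from which observation time starts; that use after end of treatment and after the switch to asciminib lies outside the window; and how patients randomized but not treated enter the denominator, since they may have no defined observation time. A model-based rate ratio with log observation time as offset is optional. It assumes a constant rate and cannot take zero follow-up.

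The cost is a paragraph of SAP text and one more table, from event counts and dates the trial should already hold. The addendum is dated after the database lock for the primary analysis, so for the primary report the addition would be post hoc and should be labelled so. For the end-of-study-treatment report it can be specified in advance if that database is not yet locked.
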